5.1.4 ICE Prophylaxis Regimen

Routine anti-emetic prophylaxis regimen should be administered with each cycle of ICE per institutional standard and should include oral or IV dexamethasone at a dose of at least 12 mg on Day 1 and 8 mg on Days 2 and 3. Omission or discontinuation of steroid antiemetic treatment may be allowed under certain circumstances (e.g., in the setting of intolerance, contraindication, or toxicity secondary to dexamethasone) upon discussion with the medical monitor.

Patients should receive prophylactic growth factor support (e.g. filgrastim [Neupogen®], a recombinant form of G-CSF, or polyethylene glycol [PEG]-filgrastim, per institutional standard) following each cycle of chemotherapy to shorten the duration of neutropenia. As per National Comprehensive Cancer Network (NCCN) guidelines, it is recommended that:

- PEG-filgrastim be given as 1 dose of 6 mg subcutaneously (s.c.) per cycle, administered the day after completion of chemotherapy
- Filgrastim be given as a daily dose of 5 mcg/kg (total dose rounded to the nearest vial size per institutional-defined weight limits) initiated the next day or up to 3-4 days after completion of chemotherapy until post-nadir ANC recovery to normal or near normal levels by laboratory standards. The preferred route of administration is s.c., but may also be given IV.

Refer to the United States Prescribing Information (USPI) for the applicable growth factor support in order to determine the appropriate administration window for use with cytotoxic chemotherapy.

Patients should also receive levofloxacin, acyclovir, and fluconazole for 10 days, or per institution guidelines.

There are no protocol-required pre- or postmedications for etoposide, ifosfamide, or carboplatin, other than those mentioned above.

5.1.5 Treatment Schedule

For a tabular view of the treatment, monitoring, and follow-up schedule, see study calendar in Section 10. Cycle length is 21 days for NIVO + ICE and 14 days for Nivolumab only.

| | | |
|--|-----------|-----|
| | Nivolumab | ICE |
|--|-----------|-----|

| | | |
|---|---|--|
| Nivolumab only | 240 mg IV every 2 weeks for 6 or 12 weeks. | N/A |
| NIVO + ICE stage, Dose Level 1 | 240 mg IV every 3 weeks (to synchronize with the ICE schedule) for 6 weeks on D1 | Ifosfamide 5000 mg/m ² IV on Day 2 Carboplatin AUC 5 IV on Day 2 Etoposide 100 mg/m ² IV on Days 1-3 |
| NIVO + ICE stage DoseLevel -1 (De-escalation) | 240 mg IV at 3 weeks and 6 weeks on Day 1 | ICE to begin on Day 8 instead of Day 1 |
| Cohort B – 1 dose Nivolumab, then NIVO + ICE | 240 mg IV at week 1, then week 3 (Cycle 2), week 6 (Cycle 3), optional week 9 (Cycle 4) | ICE to begin at week 3/Cycle 2 |

Nivolumab only and NIVO + ICE dosing can be given during a window of ± 3 day due to scheduling issues.

Criteria for dose de-escalation in the 6-patient safety monitoring cohort for patients treated with nivolumab plus ICE (cycle 1): If $\leq 1/6$ patients experience unacceptable toxicity, then the study will continue. If 2 or more patients experience unacceptable toxicity, we will stagger the dose of nivolumab and ICE by 1 week so that nivolumab will start on day 1 and ICE will start on day 8 of a 21 day cycle. There will then be another 6 patient cohort added to the monitoring. If $\leq 1/6$ patients experience unacceptable toxicity in the staggered cohort, then the study will continue. If, however, 2 or more patients experience unacceptable toxicity in the staggered cohort, then nivolumab will not be given in combination with ICE.

5.2 Definition of Unacceptable Toxicity

Unacceptable toxicity in a given patient is defined as any hematologic or non-hematologic grade 3/4 toxicity that does not resolve to a grade 1/2 within 14 days per NCI CTCAE v4.03 toxicity criteria and is considered at least possibly related to nivolumab and/or NIVO + ICE, or any other regimen-related cause of death.

5.3 Criteria for Discontinuation of Therapy

Disease progression, intolerable AEs, non-compliance, or patient withdraws consent.

5.4 Planned Duration of Therapy

5.4.1 Original trial design (Cohort A)

Nivolumab will begin as single agent for 6-12 weeks, depending on interim response rate. The nivolumab and ICE combination arm will be given for 6 weeks (max 2 cycles only).

5.4.2 Cohort B

To be enrolled only after Cohort A is completed. Nivolumab will be given as single agent for 2 weeks. The nivolumab and ICE combination arm will be given for 6-9 weeks (max 3 cycles, i.e. 9 weeks).

5.5 Subject Follow-Up

Patients will be followed for the duration of active treatment per treatment visit. After end of treatment, patient will be followed every 6 months (+/- 2 months) for survival until withdrawal of consent, death, or

study closure. Patients that discontinue study treatment due to disease progression or toxicity, or experience disease progression after the completion of treatment will remain on study for survival follow up. Patients enrolled to cohort A and B prior to Amendment 14 will remain in survival follow-up until 2 years after the last enrolled patient has completed treatment or autologous HCT. Survival follow up data will be collected by electronic medical records (EMR), telephone, email or public records. Evidence of clinical progression mentioned by patient/family member or documented in EMR need to be reviewed and collected at each timepoint if patient has yet to progress after ending treatment.

5.6 Supportive Care, Other Concomitant Therapy, Prohibited Medications

Use of neutrophil growth factors or biosimilars is mandatory when ICE is given per institutional policy and the American Society of Clinical Oncology (ASCO) guidelines. Transfusions may be given in accordance with institutional policy.

5.6.1 Management of Nivolumab Infusion Reactions

Since nivolumab contains only human immunoglobulin protein sequences, it is unlikely to be immunogenic and induce infusion or hypersensitivity reactions. However, if such a reaction were to occur, it might manifest with fever, chills, rigors, headache, rash, pruritis, arthralgias, hypo- or hypertension, bronchospasm, or other symptoms of allergic-like reactions.

All Grade 3 or 4 infusion reactions should be reported as an SAE if criteria are met. Infusion reactions should be graded according to NCI CTCAE 4.03 guidelines.

Treatment recommendations are provided below and may be modified based on local treatment standards and guidelines as appropriate:

For Grade 1 symptoms: (Mild reaction; infusion interruption not indicated; intervention not indicated): Remain at bedside and monitor subject until recovery from symptoms. The following prophylactic premedications are recommended for future infusions: diphenhydramine 50 mg (or equivalent) and/or paracetamol 325 to 1000 mg (acetaminophen) at least 30 minutes before additional nivolumab administrations.

For Grade 2 symptoms: (Moderate reaction requires therapy or infusion interruption but responds promptly to symptomatic treatment [e.g., antihistamines, non-steroidal anti-inflammatory drugs, narcotics, corticosteroids, bronchodilators, IV fluids]; prophylactic medications indicated for 24 hours).

Stop the nivolumab infusion, begin an IV infusion of normal saline, and treat the subject with diphenhydramine 50 mg IV (or equivalent) and/or paracetamol 325 to 1000 mg (acetaminophen); remain at bedside and monitor subject until resolution of symptoms. Corticosteroid or bronchodilator therapy may also be administered as appropriate. If the infusion is interrupted, then restart the infusion at 50% of the original infusion rate when symptoms resolve; if no further complications ensue after 30 minutes, the rate may be increased to 100% of the original infusion rate. Monitor subject closely. If symptoms recur then no further nivolumab will be administered at that visit. Administer diphenhydramine 50 mg IV, and remain at bedside and monitor the subject until resolution of symptoms. The amount of study drug infused must be recorded on the electronic case report form (eCRF). The following prophylactic premedications are recommended for future infusions: diphenhydramine 50 mg (or equivalent) and/or paracetamol 325 to 1000 mg (acetaminophen) should be administered at least 30 minutes before additional nivolumab administrations. If necessary, corticosteroids (recommended dose: up to 25 mg of IV hydrocortisone or equivalent) may be used.

For Grade 3 or Grade 4 symptoms: (Severe reaction, Grade 3: prolonged [i.e., not rapidly responsive to symptomatic medication and/or brief interruption of infusion]; recurrence of symptoms following initial

improvement; hospitalization indicated for other clinical sequelae [e.g., renal impairment, pulmonary infiltrates]). Grade 4: (life threatening; pressor or ventilatory support indicated).

Immediately discontinue infusion of nivolumab. Begin an IV infusion of normal saline, and treat the subject as follows. Recommend bronchodilators, epinephrine 0.2 to 1 mg of a 1:1,000 solution for subcutaneous administration or 0.1 to 0.25 mg of a 1:10,000 solution injected slowly for IV administration, and/or diphenhydramine 50 mg IV with methylprednisolone 100 mg IV (or equivalent), as needed. Subject should be monitored until the investigator is comfortable that the symptoms will not recur. Nivolumab will be permanently discontinued. Investigators should follow their institutional guidelines for the treatment of anaphylaxis. Remain at bedside and monitor subject until recovery from symptoms.

In the case of late-occurring hypersensitivity symptoms (e.g., appearance of a localized or generalized pruritis within 1 week after treatment), symptomatic treatment may be given (e.g., oral antihistamine, or corticosteroids).

6 Anticipated Adverse Event List

6.1 Nivolumab

Per the IB (version 19, June 2020) the expected toxicities for nivolumab are as follows:

| System Organ Class | Adverse Reactions |
|--|--|
| Cardiac disorders | |
| Rare | Atrial fibrillation, pericardial effusion, pericarditis, myocarditis, arrhythmia, ventricular arrhythmia |
| Very rare | |
| Endocrine disorders | |
| Uncommon | Adrenal insufficiency, hyperglycemia, hypophysitis, hypothyroidism |
| Rare | Hyperthyroidism, hypopituitarism, diabetes mellitus, diabetic ketoacidosis, Type 1 diabetes mellitus, fulminant type 1 diabetes Mellitus, autoimmune thyroiditis |
| Very rare | Autoimmune hypothyroidism, thyroiditis |
| Eye disorders | |
| Rare | Iridocyclitis, uveitis |
| Gastro-intestinal disorders | |
| Uncommon | Diarrhea, colitis, nausea, vomiting, pancreatitis |
| Rare | Autoimmune colitis abdominal pain, gastritis, stomatitis, enteritis, enterocolitis, autoimmune pancreatitis, pancreatitis acute |
| Very rare | Constipation |
| General disorders and administration site conditions | |
| Uncommon | Pyrexia, fatigue |
| Rare | Asthenia, chills, mucosal inflammation, peripheral edema |
| Hepatobiliary disorders | |
| Uncommon | Autoimmune hepatitis, hepatitis |
| Rare | Immune-mediated hepatitis, drug-induced liver injury, hepatitis acute, hyperbilirubinemia |
| Very rare | Hypertransaminasemia |

| System Organ Class | Adverse Reactions |
|---|--|
| Immune system disorders | |
| Uncommon | Infusion-related reaction, |
| Rare | Hypersensitivity, anaphylactic reaction, sarcoidosis |
| Infections and infestations | |
| Rare | Bronchitis, upper respiratory tract infection |
| Investigations | |
| Uncommon | Increased ALT, increased AST |
| Rare | Increased lipase, increased transaminases, increased liver function test, increased amylase, increased blood bilirubin, increased blood creatinine, increased blood alkaline phosphatase |
| Very rare | Increased blood glucose |
| Metabolism and nutrition disorders | |
| Uncommon | Hyponatremia |
| Rare | Dehydration, decreased appetite |
| Musculoskeletal and connective tissue disorders | |
| Rare | Myositis, arthritis, polyarthritis, myalgia, arthralgia, back pain, polymyalgia rheumatica, polymyositis, rhabdomyolysis |
| Nervous system disorders | |
| Rare | Headache, myasthenia gravis, dizziness, encephalitis, Guillain-Barre syndrome, peripheral motor neuropathy, demyelination, peripheral neuropathy, peripheral sensory neuropathy, myasthenic syndrome |
| Very rare | Polyneuropathy |
| Renal and urinary disorders | |
| Uncommon | Acute kidney injury |
| Rare | Tubulointerstitial nephritis, renal failure, autoimmune nephritis, immune-mediated nephritis |
| Very Rare | Nephritis |
| Respiratory, thoracic and mediastinal disorders | |
| Common | Pneumonitis |
| Uncommon | Interstitial lung disease, dyspnea |
| Rare | Respiratory failure, organising pneumonia, cough, immune-mediated pneumonitis |
| Skin and subcutaneous tissue disorders | |
| Rare | Rash, rash maculo-papular, pemphigoid, Stevens-Johnson syndrome, erythema multiforme, psoriasis, dermatitis, drug eruption, pruritus, rash generalized, rash papular, rash pustular |
| Very rare | Rash macular, rash pruritic, Toxic epidermal necrolysis |
| Vascular disorders | |
| Rare | Hypotension |

Adverse reactions reported for patients treated with nivolumab monotherapy (N = 14,192). Frequencies are defined as: very common ($\geq 1/10$); common ($\geq 1/100$ to $< 1/10$); uncommon ($\geq 1/1,000$ to $< 1/100$); rare ($\geq 1/10,000$ to $< 1/1,000$); very rare ($< 1/10,000$).

6.2 Ifosfamide

In clinical trials of ifosfamide monotherapy, the most common ($\geq 10\%$) adverse reactions were alopecia, nausea/vomiting, leukopenia, anemia, CNS toxicity, hematuria, and infection.

According to the package insert for ifosfamide, ifosfamide can cause:

- *Myelosuppression*: Can be severe and lead to fatal infections.
- *Neurotoxicity*: Severe and fatal neurotoxicity can occur. Carefully monitor the patient for CNS toxicity and other neurotoxic effects.
- *Urotoxicity*: Severe nephrotoxicity with renal failure and death can occur. Monitor for nephrotoxicity with serum and urine chemistries. Mesna should be used to reduce hemorrhagic cystitis.
- *Cardiotoxicity*: Arrhythmias, other ECG changes, and cardiomyopathy can occur and result in death. Use with caution in patients with cardiac risk factors and in patients with preexisting cardiac disease. The risk of cardiotoxicity is dose dependent.
- *Pulmonary toxicity*: Interstitial pneumonitis, pulmonary fibrosis, and other forms of pulmonary toxicity with fatal outcomes can occur. Monitor for signs and symptoms of pulmonary toxicity and treat as clinically indicated.
- *Secondary malignancies* as late sequelae have occurred.
- *Veno-occlusive Liver Disease*.
- *Pregnancy*: Can cause fetal harm. Women should not become pregnant and men should not father a child during therapy.
- *Effects on Fertility*: Sterility may be irreversible in some patients.
- *Anaphylactic/anaphylactoid reactions* have been reported.
- *Impairment of wound healing*.
- *Nursing*: Ifosfamide is excreted in breast milk.

6.3 Carboplatin

According to the package insert for carboplatin, carboplatin can cause:

- *Hematologic Toxicity*: Bone marrow suppression is the dose-limiting toxicity of carboplatin. Thrombocytopenia with platelet counts below $50,000/\text{mm}^3$ occurs in 25% of the patients; neutropenia with granulocyte counts below $1000/\text{mm}^3$ occurs in 16% of the patients; leukopenia with WBC counts below $2000/\text{mm}^3$ occurs in 15% of the patients. The nadir usually occurs about day 21 in patients receiving single-agent therapy. By day 28, 90% of patients have platelet counts above $100,000/\text{mm}^3$; 74% have neutrophil counts above $2000/\text{mm}^3$; 67% have leukocyte counts above $4000/\text{mm}^3$.

Anemia with hemoglobin less than 11 g/dL has been observed in 71% of the patients who started therapy with a baseline above that value. The incidence of anemia increases with increasing exposure to carboplatin. Transfusions have been administered to 26% of the patients treated with carboplatin.

Bone marrow depression may be more severe when carboplatin is combined with other bone marrow suppressing drugs or with radiotherapy.

- *Gastrointestinal Toxicity*: Vomiting occurs in 65% of the patients and in about one-third of these patients it is severe. Nausea alone occurs in an additional 10 to 15% of patients. Both nausea and vomiting usually cease within 24 hours of treatment and are often responsive to antiemetic measures.

Emesis was increased when carboplatin was used in combination with other emetogenic compounds. Other gastrointestinal effects observed frequently were pain, in 17% of the patients; diarrhea, in 6%; and constipation, also in 6%.

- *Neurologic Toxicity:* Peripheral neuropathies have been observed in 4% of the patients receiving carboplatin with mild paresthesias occurring most frequently. Clinical ototoxicity and other sensory abnormalities such as visual disturbances and change in taste have been reported in only 1% of the patients. Central nervous system symptoms have been reported in 5% of the patients and appear to be most often related to the use of antiemetics.
- *Nephrotoxicity:* Development of abnormal renal function test results is uncommon, despite the fact that carboplatin, unlike cisplatin, has usually been administered without high-volume fluid hydration and/or forced diuresis. The incidences of abnormal renal function tests reported are 6% for serum creatinine and 14% for blood urea nitrogen (10% and 22%, respectively, in pretreated ovarian cancer patients). Most of these reported abnormalities have been mild and about one-half of them were reversible.
- *Hepatic Toxicity:* The incidences of abnormal liver function tests in patients with normal baseline values were reported as follows: total bilirubin, 5%; SGOT, 15%; and alkaline phosphatase, 24%; (5%, 19%, and 37%, respectively, in pretreated ovarian cancer patients). These abnormalities have generally been mild and reversible in about one-half of the cases, although the role of metastatic tumor in the liver may complicate the assessment in many patients.
- *Electrolyte Changes:* The incidences of abnormally decreased serum electrolyte values reported were as follows: sodium, 29%; potassium, 20%; calcium, 22%; and magnesium, 29%.
- *Allergic Reactions:* Hypersensitivity to carboplatin has been reported in 2% of the patients. These allergic reactions have been similar in nature and severity to those reported with other platinum-containing compounds, ie, rash, urticaria, erythema, pruritus, and rarely bronchospasm and hypotension. Anaphylactic reactions have been reported as part of postmarketing surveillance. These reactions have been successfully managed with standard epinephrine, corticosteroid, and antihistamine therapy.
- *Injection Site Reactions:* Injection site reactions, including redness, swelling, and pain, have been reported during postmarketing surveillance. Necrosis associated with extravasation has also been reported.
- *Other Events:* Pain and asthenia were the most frequently reported miscellaneous adverse effects; their relationship to the tumor and to anemia was likely. Alopecia was reported (3%). Cardiovascular, respiratory, genitourinary, and mucosal side effects have occurred in 6% or less of the patients. Cardiovascular events (cardiac failure, embolism, cerebrovascular accidents) were fatal in less than 1% of the patients and did not appear to be related to chemotherapy. Cancer-associated hemolytic uremic syndrome has been reported rarely.
- Malaise, anorexia and hypertension have been reported as part of postmarketing surveillance.
- *Pregnancy:* Carboplatin may cause fetal harm when administered to a pregnant woman. Carboplatin has been shown to be embryotoxic and teratogenic in rats. There are no adequate and well-controlled studies in pregnant women.

6.4 Etoposide

The most common adverse reaction is neutropenia.

According to the package insert for etoposide, etoposide can cause:

- *Myelosuppression*: Etoposide causes myelosuppression that results in thrombocytopenia and neutropenia. Fatal infections and bleeding have occurred.
- *Secondary Leukemias*: Secondary leukemias have occurred with long term use of etoposide.
- *Hypersensitivity Reactions*: Etoposide can cause hypersensitivity reactions, including rash, urticaria, pruritus, and anaphylaxis.
- *Embryo-Fetal Toxicity*: Based on animal studies and its mechanism of action, etoposide can cause fetal harm when administered to a pregnant woman.
- *Lactation*: There is no information regarding the presence of etoposide in human milk or its effects on breastfed infant milk production. There is a potential for serious adverse reactions in nursing infants from etoposide.
- *Infertility*: Etoposide may result in permanent loss of fertility.
- *Gastrointestinal Toxicity*: Nausea and vomiting are the major gastrointestinal toxicities. The severity of nausea and vomiting is generally mild to moderate, with treatment discontinuation required in 1% of patients.

Other clinically important adverse reactions in clinical trials were:

- *Gastrointestinal*: abdominal pain, constipation, dysphagia.
- *General*: fever.
- *Ocular*: transient cortical blindness, optic neuritis.
- *Respiratory*: interstitial pneumonitis/pulmonary fibrosis.
- *Skin*: pigmentation, radiation recall dermatitis, Stevens-Johnson syndrome, and toxic epidermal necrolysis.
- *Neurologic*: seizure, aftertaste.

Hepatobiliary disorder: hepatotoxicity.

7 Dose Modification for Adverse Events

7.1 Dose Delay Criteria for nivolumab alone

Because of the potential for clinically meaningful nivolumab-related AEs requiring early recognition and prompt intervention, management algorithms have been developed for suspected AEs of selected categories.

Dose delay criteria apply for all drug-related adverse events (regardless of whether or not the event is attributed to nivolumab). All study drugs must be delayed until treatment can resume.

Nivolumab administration should be delayed for the following:

Any Grade ≥ 2 non-skin, drug-related AE, with the following exceptions:

- Grade 2 drug-related fatigue or laboratory abnormalities do not require a treatment delay
- Any Grade 3 drug-related skin AE

Any Grade 3 drug-related laboratory abnormality, with the following exceptions for lymphopenia, leukopenia, AST, ALT, total bilirubin, or asymptomatic amylase or lipase:

- Grade 3 lymphopenia or leukopenia does not require dose delay.

- If a subject has a baseline AST, ALT, or total bilirubin that is within normal limits, delay dosing for drug-related Grade ≥ 2 toxicity.
- If a subject has baseline AST, ALT, or total bilirubin within the Grade 1 toxicity range, delay dosing for drug-related Grade ≥ 3 toxicity.
- Any Grade ≥ 3 drug-related amylase or lipase abnormality that is not associated with symptoms or clinical manifestations of pancreatitis does not require dose delay. The Investigator should be consulted for such Grade ≥ 3 amylase or lipase abnormalities.

Any AE, laboratory abnormality, or intercurrent illness which, in the judgment of the investigator, warrants delaying the dose of study medication.

Subjects who require delay of nivolumab should be re-evaluated weekly or more frequently if clinically indicated and resume nivolumab dosing when re-treatment criteria are met.

7.2 Dose Delay Criteria for NIVO + ICE

Dose delays for NIVO + ICE are allowed under the following criteria:

- Hematological toxicity: Platelets $\leq 75,000$, Hemoglobin ≤ 8.5 , ANC $\leq 1,500$
- Non-hematological toxicity: All drug-related grade 3/4 AEs. These AEs need to resolve to grade 2 or lower before NIVO + ICE is given.

A delay of up to 14 days is allowed. After 14 days of delay, patients must be taken off the trial.

Filgrastim/packed red blood cells/platelet transfusions are allowed during this period, even during DLT assessment, as ICE therapy itself is supported by these transfusions.

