7.3 Criteria to Resume Treatment

Subjects may resume treatment with study drug when the drug-related AE(s) resolve to Grade ≤ 1 or baseline value, with the following exceptions:

- Subjects may resume treatment in the presence of Grade 2 fatigue
- Subjects who have not experienced a Grade 3 drug-related skin AE may resume treatment in the presence of Grade 2 skin toxicity
- Subjects with baseline Grade 1 AST/ALT or total bilirubin who require dose delays for reasons other than a 2-grade shift in AST/ALT or total bilirubin may resume treatment in the presence of Grade 2 AST/ALT OR total bilirubin
- Subjects with combined Grade 2 AST/ALT AND total bilirubin values meeting discontinuation parameters should have treatment permanently discontinued
- Drug-related pulmonary toxicity, diarrhea, or colitis must have resolved to baseline before treatment is resumed. Subjects with persistent Grade 1 pneumonitis after completion of a steroid taper over at least 1 month may be eligible for retreatment if Investigator allows.
- Drug-related endocrinopathies adequately controlled with only physiologic hormone replacement may resume treatment if Investigator allows.

If the criteria to resume treatment are met, the subject should restart treatment at the next scheduled timepoint per protocol. However, if the treatment is delayed past the next scheduled timepoint per protocol, the next scheduled timepoint will be delayed until dosing resumes.

If treatment is delayed or interrupted for > 6 weeks, the subject must be permanently discontinued from study therapy, except as specified in the discontinuation criteria below.

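### Sections 7.2 and 7.3 set different re-dosing conditions for NIVO + ICE after a grade 3 skin or diarrhoea/colitis event, and no text says which governs

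*Combined protocol and SAP*

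**What the plan says.** Section 7.2, headed for NIVO + ICE, allows a delay for drug-related grade 3/4 non-haematologic events and gives this condition for dosing: "These AEs need to resolve to grade 2 or lower before NIVO + ICE is given". It caps the delay at 14 days: "After 14 days of delay, patients must be taken off the trial".

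Section 7.3 has a general heading. Its rule is: "Subjects may resume treatment with study drug when the drug-related AE(s) resolve to Grade ≤ 1 or baseline value", with listed exceptions and additions. On skin: "Subjects who have not experienced a Grade 3 drug-related skin AE may resume treatment in the presence of Grade 2 skin toxicity". On lung and bowel: "Drug-related pulmonary toxicity, diarrhea, or colitis must have resolved to baseline before treatment is resumed". Its delay limit is longer: "If treatment is delayed or interrupted for > 6 weeks, the subject must be permanently discontinued from study therapy", apart from exceptions in 7.5.

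Section 7.1, headed for nivolumab alone, delays dosing for "Any Grade ≥ 2 non-skin, drug-related AE" (with exceptions), adds "All study drugs must be delayed until treatment can resume", and sends the site on to re-treatment criteria. Section 7.5 ends treatment for grade 3 non-skin events lasting more than 7 days, for some grade 3 events (pneumonitis among them) at any duration, and for most grade 4 events.

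**The concern.** A site deciding whether to give the next NIVO + ICE cycle can read 7.2 and find its condition met, while 7.3 tells it to wait. Section 7.3 speaks of study drug without defining the term. Nivolumab is study drug on any reading, and it is part of every NIVO + ICE cycle. No sentence confines 7.3 to the nivolumab-only stage or lets 7.2 override it.

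What is at stake is re-exposure to a PD-1 antibody, together with chemotherapy, while a skin or bowel event is still at grade 2. With four participating sites, the same patient could be dosed at one and held at another. Section 12.1.1 says the combination had not been tested before and that Cohort B was added because its toxicities could not yet be adequately characterised. That is a reason for a single rule.

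**Working it through.** The plan has no figure to reproduce here; the check is a comparison of texts. Each row is a patient's state on the planned NIVO + ICE day.

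| State | 7.2 | 7.3 | 7.5 | Result |
|---|---|---|---|---|
| Grade 3 skin event, now grade 2 | Met | Not met, unless baseline was grade 2; the skin allowance excludes a prior grade 3 | 7-day rule is non-skin only | Open |
| Grade 3 diarrhoea/colitis, now grade 2, 7-day rule not met | Met | Not met; baseline required | Not triggered | Open |
| Grade 3 diarrhoea/colitis that met the 7-day rule | – | – | Treatment ends | Closed |
| Grade 3 pneumonitis | – | – | Treatment ends at any duration | Closed |
| Grade 3 fatigue, now grade 2, not ended by 7.5 | Met | Met; grade 2 fatigue is allowed | Not triggered | Sections agree |
| Grade 2 diarrhoea from Cohort B Cycle 1, never grade 3 | Not listed | Baseline required, reached through the 7.1 hold | Not triggered | Held |

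The general thresholds also differ by one grade for other short-lived grade 3 non-skin events, but 7.3 attaches no organ-specific condition to those.

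**Illustration (hypothetical).** Colitis starts on Day 17 of a 21-day NIVO + ICE cycle, is grade 3 on Days 17 to 19, and is grade 2 on Day 22, the next planned Day 1. Elapsed time is 22 − 17 = 5 days, so 7.5's rule of more than 7 days is not met, whether it counts time at grade 3 or total duration. Section 7.2's condition is met; 7.3 requires baseline.

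**Size of the gap**
- Skin: grade 2 − grade 1 = 1 grade.
- Diarrhoea/colitis: grade 2 − grade 0 = 2 grades, assuming baseline grade 0.
- Delay limit: 6 × 7 = 42 days in 7.3 against 14 in 7.2, a difference of 28 days.

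**Reach.** Section 12.1.1 gives a maximum of 35 Cohort B patients, 13 of them treated by the April 2021 update, and 2 to 3 NIVO + ICE cycles each. Cohort B enrols only after Cohort A is complete (5.4.2).
- Patients: 35 − 13 = 22 at most.
- NIVO + ICE dosing days: 22 × 2 = 44 to 22 × 3 = 66.
- Of these, 22 are first combination doses at Cycle 2 Day 1. Doses that follow an earlier NIVO + ICE cycle number 44 − 22 = 22 to 66 − 22 = 44.

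**The case against.** The strongest reply is that 7.2 is self-contained. It is headed for this regimen and has its own threshold and its own 14-day limit. Section 7.1 points on to re-treatment criteria and 7.2 does not. Section 7.3's 6-week limit and its steroid taper of at least a month do not fit a 14-day window. That reading is plausible, but it is not written down.

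A second reply is that a site applying 7.3 satisfies both thresholds. That is correct, so a reader who infers that the two sections cannot both be obeyed goes too far. What is missing is a statement of precedence.

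A reader might also infer that the conflict is sharpest at Cohort B Cycle 2 Day 1, where every patient passes from nivolumab alone to NIVO + ICE. The documents do not support this well. An event arising in Cycle 1 falls under 7.1, which holds all study drugs until re-treatment criteria are met, and those criteria are in 7.3. Section 7.2 does not lift a hold already in force, and an event that it does not list is not thereby cleared for dosing. The better reading is that 7.1 and 7.3 already govern there.

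Finally, investigators may delay (7.1) or discontinue (7.5) on their own judgement, and 7.4 refers them to management algorithms. Judgement is a real safeguard, though it sets no common threshold. The algorithms are in the Investigator's Brochure, which is not among the documents, so no claim is made about their content.

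**Conclusion.** The point holds as a minor safety harmonisation. Sections 7.2 and 7.3 give different answers for two cases that 7.5 leaves open, and no text settles which applies. This is more than missing detail: 7.2 taken alone permits nivolumab with grade 2 colitis that 7.3 forbids. The open cases lie mainly within NIVO + ICE cycles; the Cohort B handover needs only a confirming cross-reference.

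The reach of 22 patients and 44 to 66 dosing days is an upper bound. It assumes that Cohort B fills to 35, that each remaining patient receives 2 to 3 combination cycles, and that new wording arrives before any of them is treated.

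A reader might want to turn this into an expected number of affected patients from Section 6.1 or 2.2.4. The documents do not support that. The frequencies in 6.1 are for monotherapy and class rash as rare, whereas 2.2.4 reports drug-related rash in 22% of patients in the phase I Hodgkin trial; neither figure is for the combination. Nor do the documents support a reading that the discrepancy affects error rates, power or sample size.

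**What to change.** Amend 7.2 as follows.

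- Before nivolumab is given with ICE, drug-related diarrhoea or colitis must be back to baseline, and a prior grade 3 skin event must be at grade 1 or lower, or at baseline, as in 7.3.
- Keep 7.2's grade 2 threshold for other non-haematologic events unless the sponsor chooses otherwise. A blanket grade 1 rule for chemotherapy toxicity would hold more patients and is not recommended by default.
- State that 7.2's 14-day limit overrides 7.3's 6 weeks for NIVO + ICE. Section 7.2 already imposes the limit; a half-sentence removes the doubt.
- Add a cross-reference confirming that events carried from Cycle 1 into Cohort B Cycle 2 Day 1 follow the 7.1 hold and the 7.3 criteria.

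The cost is protocol wording, with no added patients or procedures. The downside is that a few patients may be held longer, and some may come off trial when the 14 days run out.
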